#### **11.5 Data Analyses**

All data will be analyzed using SPSS 22.0 for Windows (SPSS Inc. Chicago, IL, USA) by a professional statistician at St. Michael's hospital.

### **12 Data Management**

#### **12.1 Source documents**

Source documents are the subject records maintained at the study site. In most cases, the source documents will be the physician's or hospital's subject chart. In some cases, the source documents may be electronic. In both cases, the information captured in the CRF must match the information in the chart or electronic source document. The Investigator agrees to make source documents (hard copy or electronic) available for monitoring by the Sponsor and/or their representatives.

### **13 Data Collection, Processing, and Review**

Subject data will be recorded in a limited access secure data system.

See Section 10 of this protocol for a description of how video and audio feeds for each surgical procedure will be stored.

Other, non-video and –audio datacollected as part of this study will reside on a production server hosted by an electronic data capture (EDC) System. The Simplified Clinical Data Systems LLC (Simplified) is a provider of fully FDA compliant, responsive clinical data management services, providing a globally accessible hosted platform that meets stringent security and reliability standards.

CDP operates from SSAE16, HIPAA, SOC I/SOC II, compliant data centers in Marlborough, MA, and Tek Park (Allentown), PA. Nightly, offsite backups are mirrored and maintained at Iron Mountain's two underground data centers.

The Network Operations Center (NOC) monitors these systems 7x24x365 with a team of network engineers ensuring system availability and data integrity.

Systems and processes are well documented and have stood up to thorough scrutiny by sponsor and third party audits, for compliance with U.S. and EU standards.

This platform will be maintained by Olympus Corporation.

All changes made to the clinical data will be captured in an electronic audit trail and available for review by the Sponsor or its representative. The associated software and database have been designed to meet regulatory compliance for deployment as part of a validated system compliant with laws and regulations applicable to the conduct of clinical studies pertaining to the use of electronic records and signatures. Database backups are performed regularly

The Investigator provides his/her electronic signature on the appropriate electronic case report forms (eCRFs) in compliance with local regulations. A written signature on printouts of the eCRFs must also be provided if required by local regulation. Changes to data previously submitted to the Sponsor require a new electronic signature by the Investigator acknowledging and approving the changes.

Data entered into the EDC system will be reviewed to identify possible data discrepancies. Manual and/or automatic queries will be created by the Sponsor in the EDC system and will be issued to the site for appropriate response. Site staff will be responsible for resolving all queries in the database.

## **14 Data Retention**

The Principal Investigator or his/her designee or Investigational site will maintain, at the investigative site, all essential study documents and source documentation that support the data collected on the study subjects in compliance with ICH/GCP guidelines. Documents must be retained for at least 2 years have elapsed since the formal discontinuation of the clinical investigation of the product. These documents will be retained for a longer period of time by agreement with Olympus or in compliance with other country/regional/local regulations.

The Principal Investigator or his/her designee will take measures to ensure that these essential documents are not accidentally damaged or destroyed. If for any reason the Principal Investigator or his/her designee withdraws responsibility for maintaining these essential documents, custody must be transferred to an individual who will assume responsibility and Olympus must receive written notification of this custodial change. Sites

are required to inform Olympus in writing where paper or electronic files are maintained in case files are stored off site and are not readily available.

## **15 Amendments**

If a protocol revision is necessary which affects the rights, safety or welfare of the subject or scientific integrity of the data, an amendment is required. Appropriate approvals (e.g., REB) of the revised protocol must be obtained prior to implementation.

## **16 Deviations**

An Investigator must not make any changes or deviate from this protocol, except to protect the life and physical well-being of a subject in an emergency. An Investigator shall notify the Sponsor and the reviewing REC of any deviation from the investigational plan to protect the life or physical well-being of a subject in an emergency, and those deviations which affect the scientific integrity of the clinical investigation. Such notice shall be given as soon as possible, but no later than 5 working days after the emergency occurred, or per prevailing local requirements, if sooner than 5 working days.

All deviations from the investigational plan, with the reason for the deviation and the date of occurrence, must be documented and reported to the Sponsor. Sites may also be required to report deviations to the REC, per local guidelines and government regulations.

Deviations will be reviewed and evaluated on an ongoing basis and, as necessary, appropriate corrective and preventive actions (such as site re-training or site discontinuation/termination) will be put into place by the Sponsor.

## **17 Device/Equipment Accountability**

The study devices/equipment supplied by the Sponsor for this study shall be securely maintained, controlled, and used only in this clinical study.

The Sponsor shall keep records to document the physical location of all study devices/equipment from study device/equipment shipment until use, return, or disposal.

The Principal Investigator or an authorized designee shall keep records documenting the receipt, use, return and disposal of the study devices/equipment, which shall include the following

- Date of receipt
- Identification of each study device/piece of equipment (serial number or unique code)
- Expiry date, as applicable
- Date or dates of use
- Unique subject identification number
- Date of return (and number) of unused, expired, or malfunctioning study devices/equipment, as applicable.

## **18 Compliance**

### **18.1 Statement of Compliance**

This study will be conducted in accordance with ICH Guidelines, Good Clinical Practices, ISO 14155, ethical principles that have their origins in the Declaration of Helsinki, and pertinent individual country laws and regulations. The study shall not begin until the required approval/favorable opinion from the REC has been obtained. Any additional requirements imposed by the REC shall be followed, if appropriate.

## **19 Investigator Responsibilities**

The Principal Investigator of an investigational site is responsible for ensuring that the study is conducted in accordance with the Clinical Trial Agreement, the clinical investigation plan, ISO 14155, ethical principles that have their origins in the Declaration of Helsinki, any conditions of approval imposed by the reviewing IRB/EC, and prevailing local and/or country laws and/or regulations, whichever affords the greater protection to the subject.

The Principal Investigator's responsibilities include, but are not limited to, the following.

- Prior to beginning the study, sign the Clinical Trial Agreement and comply with the Investigator responsibilities as described in such Agreement.
- Prior to beginning the study, sign the Protocol Signature page documenting his/her agreement to conduct the study in accordance with the protocol.
- Provide his/her qualifications and experience to assume responsibility for the proper conduct of the study and that of key members of the site team through up-to-date curriculum vitae or other relevant documentation and disclose potential conflicts of interest, including financial, that may interfere with the conduct of the clinical study or interpretation of results.
- Make no changes in or deviate from this protocol, except to protect the life and physical well-being of a subject in an emergency; document and explain any deviation from the approved protocol that occurred during the course of the clinical investigation.
- Create and maintain source documents throughout the clinical study and ensure their availability with direct access during monitoring visits or audits; ensure that all clinical-investigation-related records are retained per requirements.
- Ensure the accuracy, completeness, legibility, and timeliness of the data reported to the Sponsor in the CRFs and in all required reports.
- Record, report (to Sponsor, and IRB as applicable), and assess every adverse event as applicable per the protocol and observed device deficiency.
- Report to the REC and regulatory authorities any SAEs and device deficiencies that could have led to a SADE and potential/USADE or UADE, if required by the national regulations or this protocol or by the IRB/EC, and supply Olympus with any additional requested information related to the safety reporting of a particular event.

- Maintain the device accountability records and control of the device, ensuring that the study device is used only by authorized/designated users and in accordance with this protocol and instructions/directions for use.
- Allow the Sponsor to perform monitoring and auditing activities, and be accessible to the clinical research monitor or auditor and respond to questions during monitoring visits or audit(s).
- Allow and support regulatory authorities and the REC when performing auditing activities.
- Ensure that informed consent is obtained in accordance with applicable laws, this protocol and local IRB/EC requirements.
- Provide adequate medical care to a subject during and after a subject's participation in a clinical study in the case of adverse events, as described in the ICF.
- Inform the subject of the nature and possible cause of any adverse events experienced.
- As applicable, provide the subject with necessary instructions on proper use, handling, storage, and return of the study device when it is used/operated by the subject.
- Inform the subject of any new significant findings occurring during the clinical investigation, including the need for additional medical care that may be required.
- Provide the subject with well-defined procedures for possible emergency situations related to the clinical study, and make the necessary arrangements for emergency treatment, including decoding procedures for blinded/masked clinical investigations, as needed.
- Ensure that clinical medical records are clearly marked to indicate that the subject is enrolled in this clinical study.
- Ensure that, if appropriate, subjects enrolled in the clinical investigation are provided with some means of showing their participation in the clinical investigation, together with identification and compliance information for concomitant treatment measures (contact address and telephone numbers shall be provided).
- Inform, with the subject's approval or when required by national regulations, the subject's personal physician about the subject's participation in the clinical investigation.
- Make all reasonable efforts to ascertain the reason(s) for a subject's premature withdrawal from clinical investigation while fully respecting the subject's rights.
- Ensure that an adequate investigation site team and facilities exist and are maintained and documented during the clinical investigation.
- Ensure that maintenance and calibration of the equipment relevant for the assessment of the clinical investigation is appropriately performed and documented, where applicable.

## **20 Delegation of Authority**

The Principal Investigator is responsible for providing appropriate training and adequate supervision of those to whom tasks are delegated. The Principal Investigator is accountable for regulatory violations resulting from failure to adequately supervise the conduct of the clinical study.

## **21 Research Ethics Committee**

The protocol and informed consent document must have the approval of a properly constituted committee (REC) responsible for approving clinical trials. The signed REC approval letter must identify the documents approved (i.e., list the Investigator's name, the protocol title, and date of approval, and informed consent document). A copy of the approval of the protocol (or permission to conduct the study) and ICF, must be received by the Sponsor before recruitment of subjects into the study and shipment of investigational product/equipment. Prior approval must also be obtained for other materials related to subject recruitment or which will be provided to the subject.

Annual REC approval and renewals will be obtained throughout the duration of the study as or as locally required. Copies of the Investigator's reports and the IRB/EC continuance of approval must be provided to the Sponsor.

## **22 Sponsor Responsibilities**

All information and data sent to Olympus concerning subjects or their participation in this study will be considered confidential by Olympus. Only authorized Olympus personnel or an Olympus representative including, but not limited to Contract Research Organization (CRO) will have access to these confidential records. Authorized regulatory personnel have the right to inspect and copy all records pertinent to this study. Study data collected during this study may be used by Olympus for the purposes of this study, publication, and to support future research and/or other business purposes. All data used in the analysis and reporting of this study will be without identifiable reference to specific subject name.

Olympus will keep subjects' identifiable health information confidential in accordance with all applicable laws and regulations. Olympus may use subjects' health information to conduct this research, as well as for additional purposes, such as overseeing and improving the performance of its device, new medical research and proposals for developing new medical products or procedures, and other business purposes. Information received during the study will not be used to market to subjects; subject names will not be placed on any mailing lists or sold to anyone for marketing purposes.

## **23 Insurance**

Where required by local/country regulation, proof and type of insurance coverage, by Olympus for subjects in the study will be obtained.

## **24 Monitoring**

On site and/or remote monitoring will be performed during the study to assess continued compliance with the protocol and applicable regulations. In addition, the clinical research monitor verifies that study records are adequately maintained, that data are reported in a satisfactory manner with respect to timeliness, adequacy, and accuracy, and that the Principal Investigator continues to have sufficient staff and facilities to conduct the study safely and effectively. The Principal Investigator/institution guarantees direct access to original source documents by Olympus personnel, their designees, and appropriate regulatory authorities.

The study may also be subject to a quality assurance audit by Olympus or its designees, as well as inspection by appropriate regulatory authorities. It is important that the Principal Investigator and relevant study personnel are available during on-site monitoring visits or audits and that sufficient time is devoted to the process.

## **25 Potential Risks and Benefits**

### **25.1 Anticipated Adverse Events**

The following anticipated AEs have been identified for this study.

### **25.2 Risks Associated with the Study Device(s)**

Incremental risks that are associated with the study device and are above those of market available products are listed below.

### **25.3 Anticipated Benefits**

There are no direct benefits from participation in this study. This study will not give you any improved treatment of any kind. There is however a potential benefit for future patients and operating room teams since the purpose of this study is to improve the training of the entire operating room team with the overall intention to improve patient safety in surgery. Results from this study may further medical or scientific knowledge.

## **26 Safety Reporting**

### **26.1 Reportable Events by Investigational Site to Olympus**

It is the responsibility of the Investigator to assess and report to Olympus any event which occurs in any of following categories:

- Clinically significant adverse events related to the device(s) and/or procedure.
  - Clinically significant is defined as any deviation from the normal surgical or post operative course that requires special treatment or action
- Device Deficiencies
- Unanticipated Adverse Device Effects/Unanticipated Serious Adverse Device Effects
- New findings/updates in relation to already reported adverse events

When possible, the medical diagnosis should be reported as the Event Term instead of individual symptoms.

If it is unclear whether or not an event fits one of the above categories, or if the event cannot be isolated from the device or procedure, it should be submitted as an AE and/or device deficiency.

Any AE experienced by a study subject during the study procedure through completion of the study must be recorded in the CRF.

Underlying diseases are not reported as AEs unless there is an increase in severity of frequency during the course of the investigation

## 26.2 Definitions and Classification

Adverse event definitions are provided in Table 2.

**Table 2: Adverse Event Definitions**

Term	Definition
Adverse Event (AE)  Ref: ISO 14155  Ref: MEDDEV 2.7/3	
Any untoward medical occurrence, unintended disease or injury, or any untoward clinical signs (including an abnormal laboratory finding) in subjects, users or other persons, whether or not related to the investigational medical device.
 
NOTE 1: This includes events related to the investigational medical device or comparator.
 
NOTE 2: This definition includes events related to the procedures involved.
 
NOTE 3: For users or other persons, this definition is restricted to events related to the investigational medical device.

Adverse Device Effect (ADE)  Ref: ISO 14155  Ref: MEDDEV 2.7/3	
Adverse event related to the use of an investigational medical device
 

• NOTE 1: This includes any adverse event resulting from insufficiencies or inadequacies in the instructions for use, the deployment, the implantation, the installation, the operation, or any malfunction of the investigational medical device.

• NOTE 2: This definition includes any event resulting from use error or intentional abnormal use of the investigational medical device.

Serious Adverse Event (SAE)  Ref: ISO 14155  Ref: MEDDEV 2.7/3	
Note: This definition meets the reporting objectives and requirements of ISO 14155 and MEDDEV 2.7/3.
 
Adverse event that:
 

• Led to death,

• Led to serious deterioration in the health of the subject as defined by either:

◦ a life-threatening illness or injury, or

◦ a permanent impairment of a body structure or a body function, or

◦ in-subject hospitalization or prolongation of existing hospitalization , or

◦ in medical or surgical intervention to prevent life-threatening

**Table 2: Adverse Event Definitions**

Term	Definition
	
illness
 
 
◦ injury or permanent impairment to a body structure or a body function
 
• Led to fetal distress, fetal death, or a congenital abnormality or birth defect.
 
 
NOTE 1: This includes device deficiencies that might have led to a serious adverse event if a) suitable action had not been taken or b) intervention had not been made or c) if circumstances had been less fortunate. These are handled under the SAE reporting system.
 
NOTE 2: A planned hospitalization for pre-existing condition, or a procedure required by the Clinical Investigation Plan, without a serious deterioration in health, is not considered to be a serious adverse event.

Serious Adverse Device Effect (SADE) Ref: ISO 14155 Ref: MEDDEV 2.7/3	
Adverse device effect that has resulted in any of the consequences characteristic of a serious adverse event.

Unanticipated Adverse Device Effect (UADE) Ref: 21 CFR Part 812	
Any serious adverse effect on health or safety or any life-threatening problem or death caused by, or associated with, a device, if that effect, problem, or death was not previously identified in nature, severity, or degree of incidence in the investigational plan or application (including a supplementary plan or application), or any other unanticipated serious problem associated with a device that relates to the rights, safety, or welfare of subjects.

Unanticipated Serious Adverse Device Effect (USADE) Ref: ISO 14155 Ref: MEDDEV 2.7/3	
Serious adverse device effect which by its nature, incidence, severity, or outcome has not been identified in the current version of the risk analysis report.
 
NOTE 1: Anticipated serious adverse device effect (ASADE) is an effect which by its nature, incidence, severity or outcome has been identified in the risk analysis report.

Device Deficiency Ref: ISO 14155 Ref: MEDDEV 2.7/3	
An inadequacy of an investigational medical device related to its identity, quality, durability, reliability, safety or performance. This may include malfunctions, use error, or inadequacy in the information supplied by the manufacturer.

### 26.3 Clavien Classification of Surgical Complications

All AEs that occur intra-operatively or within the 30 Day Follow-up period will be assessed using the CCSC:

**Grade I:** Any deviation from the normal post-operative course without the need for pharmacological treatment or surgical, endoscopic, and radiological interventions.

Allowed therapeutic regimens are: drugs as antiemetics, antipyretics, analgetics, diuretics, electrolytes, and physiotherapy. This grade also includes wound infections opened at bedside.

**Grade II:** Requiring pharmacological treatment with drugs other than such allowed for Grade I complications. Blood transfusions and total parenteral nutrition are also included.

**Grade III:** Requiring surgical, endoscopic or radiological intervention.

**Grade IIIa:** Intervention not under general anesthesia

**Grade IIIb:** Intervention under general anesthesia

**Grade IV:** Life-threatening complication (including CNS complications) requiring IC/ICU management.

**Grade IVa:** Single organ dysfunction (including dialysis)

**Grade IVb:** Multi-organ dysfunction

**Grade V:** Death of a patient

**Suffix “d”:** If the patient suffers from a complication at the time of discharge the suffix “d” (for disability) is added to the respective grade of complication. This label indicates the need for a follow-up to fully evaluate the complication.

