Follow-up Schedule	
 
1. Screening/Baseline (Clinic Visit): 
 
a. Eligibility criteria
 
b. Informed consent
 
c. Demographics
 
d. Medical history
 
 
 
2. Procedure (Hospital Visit): 
 
a. Laparoscopic 2D or 3D Roux-en-Y gastric bypass surgery
 
b. Adverse events (Including Clavien Classification of Surgical Complications (CCSC))
 
c. Device Deficiencies
 
d. Completion of STAR Questionnaire by each OR team member
 
e. NASA Task Load Index to assess mental workload and frustration
 
f. Visualization and Physical Symptoms Questionnaire
 
g. Surgical Team Demographic Questionnaire
 
 
 
3. Post-Procedure OSATS and GERT 
 
a. Post-Procedure is not a subject follow-up visit, it is the point at which the video and audio feed of each surgical procedure will be reviewed by an Expert Surgical Analyst (ESA) to complete the OSATS and GERT tools.
 
b. The ESA must review video feed within 30 days following each procedure.
 
 
 

**A Prospective, Post Market, Feasibility Study to Assess the Practical Utility of the OR BlackBox Platform When Used to Compare Surgical Technique During 3D Versus 2D Laparoscopic Bariatric Surgery - The "Black Box" Study**

	
4. 30 Day Post Procedure Follow-up (Telephone Call) / End of Study
 
 
Adverse events (Including CCSC)
 
End of study will be reached after completion of the 30 Day Post Procedure Follow-up Telephone Call, subject withdrawal, or lost to follow-up, whichever occurs first.
 

Study Duration	This study is anticipated to take 9 months to complete following IRB approval. Eight months of enrollment and 1 month of follow-up.
Key Inclusion Criteria	
 
≥ 18 years of age
 
Scheduled to undergo elective, primary roux-en-y gastric bypass surgery
 
BMI of 35 to 54.9
 
Willing and able to provide informed consent
 

Key Exclusion Criteria	
 
Previous open abdominal surgery
 
Previous open or laparoscopic upper GI surgery
 
Contraindicated for laparoscopic bariatric surgery
 
Unable or unwilling to provide informed consent
 

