## 9.2 Procedure (Hospital Visit)

- Laparoscopic 2D or 3D roux-en-y gastric bypass surgery
  - All study procedures will be video and audio recorded using 2 mounted cameras and auxilliary microphones. One camera will be focused on the surgical field and the second focusing on the OR door.
  - The laparoscopic video (internal subject view) will be recorded according to standard of practice.
  - All video and audio recordings will begin after the subject has been intubated and will end at skin closure prior to extubation.
- Procedure time (minutes) (skin-to-skin)
  - The Principal Investigator will perform the gastrojejunostomy (GJ) anastomosis
  - A surgical fellow will perform the jejunojejunostomy (JJ) anastomosis
- Adverse events (Including Clavien Classification of Surgical Complications (CCSC))
- Device deficiencies
- STAR Questionnaire will be completed by each surgical team member within 24 hours of surgical procedure

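### Section 26.3 puts intra-operative adverse events on a post-operative Clavien scale, so read literally an injury repaired during the bypass gets the same Grade IIIb as a re-operation

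*Combined protocol and SAP*

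**What the plan says.** Section 26.3 sets the scope of the Clavien Classification of Surgical Complications (CCSC): "All AEs that occur intra-operatively or within the 30 Day Follow-up period will be assessed using the CCSC". Section 9.2 and the follow-up schedule in the synopsis also list CCSC grading with the adverse events of the procedure visit, so the inclusion of intra-operative events is deliberate.

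The grades that matter here are printed in the same section:

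- Grade I: "Any deviation from the normal post-operative course without the need for pharmacological treatment or surgical, endoscopic, and radiological interventions".
- Grade II: "Requiring pharmacological treatment with drugs other than such allowed for Grade I complications", with transfusion and parenteral nutrition added.
- Grade III: "Requiring surgical, endoscopic or radiological intervention", divided into IIIa, "Intervention not under general anesthesia", and IIIb, "Intervention under general anesthesia".

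On the patient's state during surgery, section 9.2 says: "All video and audio recordings will begin after the subject has been intubated and will end at skin closure prior to extubation".

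Table 2 counts an unintended injury as an adverse event and includes events related to the procedures. Section 26.1 requires adverse events to be recorded from the study procedure onwards. The first secondary endpoint (sections 4.2 and 11.1.2) concerns clinically significant events related to device or procedure. It covers departures from the expected course both during and after surgery, and it does not refer to Clavien grade. Section 11.4 names the tests and models to be used, none of them by grade.

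**The concern.** The scale ranks a complication by the treatment it needed. That works after the operation, when a surgical intervention under general anaesthesia means a new operation. During the index operation the patient is already anaesthetised and a surgeon is already operating, so the two conditions for IIIb are met by circumstance and say little about severity.

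This matters for a 2D versus 3D comparison because the Introduction gives technical errors from impaired depth perception as the reason to study 3D. On-table events are therefore a place where the arms could plausibly differ. If repaired injuries and re-operations share one grade, a table of grades by arm cannot show whether a difference reflects events during the operation or harm to patients afterwards.

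The rule also leaves room for improvisation. The principal investigator performs the gastrojejunostomy (section 9.2), and so knows which display is in use, and is also responsible for assessing adverse events (section 19).

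**Working it through.** There is no planned figure to reproduce. The check applies the printed grades to one case: a minor, non-life-threatening unintended injury, sutured during the bypass.

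1. **Must it be recorded?** Yes. It is an adverse event under Table 2 and it occurs within the recording window of section 26.1.
2. **Must it be graded?** Yes. Section 26.3 covers all adverse events and names intra-operative ones.
3. **Which grade fits?** By elimination:
   - Grade I is excluded, because a surgical intervention was needed.
   - Grade II is excluded, because the treatment was a suture and not a drug, transfusion or parenteral nutrition.
   - Grade IIIa is excluded, because the patient was under general anaesthesia. This is inferred from the intubation and extubation wording in section 9.2, which does not name the type of anaesthesia.
   - Grade IV is excluded, because there was no life-threatening complication needing intensive care.
   - Grade V is excluded, because the patient did not die.
   - Grade IIIb is the only grade left. Its text makes no exception for anaesthesia already given for the index operation.
4. **What else gets IIIb?** A post-operative re-operation under general anaesthesia. The grade alone does not separate the two.

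**Size.** Each arm has 25 patients (section 5.1). For k patients in an arm with a repaired intra-operative injury and no other IIIb event, the IIIb proportion rises by k/25:

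- k = 1: 1/25 = 4 percentage points
- k = 2: 2/25 = 8 percentage points
- k = 3: 3/25 = 12 percentage points

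The documents give no rate for such injuries, so k is an assumption. As an illustration only, suppose 3 such patients under 2D, 1 under 3D and no re-operations. A by-arm grade table would show IIIb in 3/25 = 12% against 1/25 = 4%, while the post-operative IIIb proportion is 0/25 = 0% in both arms. The count is of patients: two repairs in the same patient still add 4 points.

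**The case against.** The strongest objection is that the harm falls on an analysis the plan does not contain. A reader might infer that the study will report Grade IIIb rates by arm. It does not say so. Grade is not an endpoint, section 11.4 plans nothing by grade, and the secondary endpoint would count a sutured injury in the same way whatever its grade. This stands, and it limits the point to descriptive reporting. The grades are nevertheless collected on every event and are the protocol's only graded severity scale, so a table of them by arm is a natural use.

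A second objection is that the protocol never itself says a sutured injury is IIIb, and that a sensible grader would treat the suture as part of the index operation. The first half is true, since the result is an inference. The second half has no text to rest on and conflicts with the instruction to grade all events.

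A third concerns consistency. A reader might also infer that an untreated intra-operative event has no grade at all, because Grade I speaks of the post-operative course. That cannot be combined freely with the IIIb argument. If section 26.3 extends the whole scale to intra-operative events, Grade I extends too, and the repaired injury is IIIb. If the scale stays post-operative throughout, the repaired injury has no grade and the instruction to grade it cannot be followed. Section 26.3 needs repair on either reading. The point made here uses the first, which is what its opening sentence says.

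Finally, other fields partly separate the events. Seriousness is classified independently in Table 2, and a re-operation that prolonged the hospital stay would be serious where a minor suture ordinarily would not. Events are also listed by visit. But section 9.2 gives no end to the hospital visit, so an early post-operative complication may sit under the same visit as an on-table repair. Neither field was designed to make this distinction.

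**Conclusion.** The point holds, with limited impact. Taken literally, section 26.3 gives an injury repaired during the index operation the same grade as a re-operation, so any by-arm summary of CCSC grades would mix the two. Each affected patient is 4 percentage points of an arm of 25. How many there would be cannot be known from the documents. The secondary endpoint itself, as a count of clinically significant related events, is not altered.

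The conclusion rests on three assumptions: that intubation implies general anaesthesia, that the repaired injury is an adverse event and not life-threatening, and that someone tabulates the grades by arm.

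Three stronger readings are not supported. A reader might extend the argument to every surgical step taken on the table, such as a clipped vessel or a reinforced staple line, but nothing in the documents says these are untoward and not part of the operation. A reader might suppose that the severity distribution would mostly reflect on-table suturing, but no frequencies are given. And a reader might suppose that the same events are counted again as errors on the Generic Error Rating Tool, but that tool's content is not printed.

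**What to change.** In section 26.3, with matching lines in section 9.2 and the synopsis:

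- Apply CCSC grades to post-operative complications, including any post-operative consequence of an intra-operative event.
- Name the moment that divides intra-operative from post-operative. Section 9.2 places skin closure before extubation, so if skin closure is chosen, say how an event treated in that interval is handled.
- Add an intra-operative flag to the AE eCRF, with a category for what the event led to. One possible set is: no added step; a repair or added step completed laparoscopically; conversion or abandonment; a post-operative consequence.
- Tabulate intra-operative events by arm in their own table, never pooled with post-operative grades.

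The cost is wording in three places and two fields on the AE form (the flag and the category), with no new assessment. The downside is that fewer events would carry a Clavien grade. If the sponsor prefers to keep grading intra-operative events, the minimum is an explicit convention in section 26.3 for events treated within the index operation, with separate tabulation.
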